## 9.1.2.5 Mixed-Meal Tolerance Test (MMTT)

Basal (fasting) and stimulated glucose and c-peptide levels will be determined using the MMTT. Subjects will be instructed not to eat or inject short-acting (or bolus) insulin after 8 PM the night before the test. Evening or bedtime administration of long-acting insulin will be permitted, as will consumption of water. Subjects receiving CSII (insulin "pump" therapy) may remain on the basal rate of insulin. Subjects will arrive fasting to the transplant or diabetes clinic where the capillary BG will be checked. If the BG is <70 mg/dL (3.89 mmol/L) or >180 mg/dL (10 mmol/L), the test will be rescheduled for the next possible day. If the BG is 70 – 180 mg/dL (3.89 – 10 mmol/L), basal glucose and c-peptide levels will be drawn. Immediately after, the subject will receive 6 mL per kg body weight (to a maximum of 360 mL) of Boost® High Protein

Drink (or a nutritionally equivalent substitute) to consume in 5 minutes starting at time = 0. Then, at time = 90 minutes, stimulated glucose and c-peptide levels will again be drawn.

Each blood sample collected for c-peptide and glucose determination will be drawn according to University of Washington (Seattle, WA) SOP and will be shipped frozen to U of W for measurement in the core laboratory.

## 9.1.2.6 **\beta-Score**: A Composite Index of Post-Transplant Graft Function

The  $\beta$ -score will be determined from the HbA1c, insulin requirements, fasting (basal), glucose, and basal or stimulated c-peptide as developed by Ryan *et al*. The score may range from 0 (no graft function) to 8, with all subjects reported with a score of 8 also having 90-minute glucose levels during a MMTT that are  $\leq$ 10.0 mmol/L (180 mg/dL), indicative of excellent graft function.

# 9.1.2.7 The C-Peptide: (Glucose X Creatinine) Ratio

The c-peptide: (glucose X creatinine) ratio (CPGCR) will be determined from the fasting (basal) glucose and c-peptide, and a simultaneous serum creatinine. This measure accounts for both the dependence of c-peptide secretion on the ambient glucose concentration and the dependence of c-peptide clearance on kidney function  $^{163, 164}$ . The CPGCR is calculated as [c-peptide (ng/mL) \* 100]/[glucose (mg/dL) \* creatinine (mg/dL)]. An index of islet graft function, this measure correlates well with both the 90-minute glucose levels during a MMTT and with the  $\beta$ -score  $^{165}$ .

# 9.1.2.8 Insulin-Modified Frequently-Sampled Intravenous Glucose Tolerance (FSIGT) Test

The AIRglu, insulin sensitivity (SI), and disposition index (DI) will be determined using the FSIGT test. This assessment provides a composite measure of  $\beta$ -cell function, the DI, which relates the effect of SI on first-phase insulin secretion (AIRglu). Understanding the effect of insulin sensitivity on insulin secretory dynamics post-transplant is important because insulin resistance imposes an increased demand on  $\beta$ -cell function to maintain the same level of glycemia. Whether insulin resistance, possibly attributable to immunosuppressive drugs, is an important problem post-transplant is not known. Preliminary data indicate that insulin sensitivity may actually be improved post-transplant, despite immunosuppression, possibly due to improved glucose and free fatty acid metabolism^152. These results require confirmation by longitudinal analysis.

The insulin-modified FSIGT test involves blood sampling at baseline (t = -10, -5, and -1 min) and at t = 1, 2, 3, 4, 5, 7, 10, 12, 14, 16, 18, 20, 22, 25, 30, 40, 50, 70, 100, 140, & 180 minutes post-injection of glucose at t = -30 seconds with an injection of insulin at t = 20 min. Each blood sample collected for insulin, c-peptide, and glucose determination will be drawn according to University of Washington (Seattle, WA) SOP and will be shipped frozen to U of W for measurement in the core laboratory. The AIRglu is calculated as the incremental area-under-the-curve for insulin between 0 and 10 minutes post-injection (the same calculation can be performed for c-peptide). Glucose effectiveness (SG), a measure of insulin-independent glucose disposal, and SI, a measure of insulin-dependent glucose disposal, are derived from Bergman's minimal model using MinMod Millenium® software, and further allow for determination of the disposition index (DI = AIRglu · SI).

# 9.1.2.9 Continuous Glucose Monitoring System® (CGMS)

Glucose variability and hypoglycemia duration will be determined using CGMS® (Medtronic Minimed, Northridge, CA). CGMS involves the SC placement of a glucose sensor connected by tubing to a pager-sized monitoring device that stores glucose data over a 72-hour period. Subjects will have the sensor placed in the diabetes clinic and wear it continuously for 72 – 84 hours. Then they will drop the monitoring device off or ship it to the clinic 4 days later for analysis. Subjects will need to calibrate the sensor to their capillary BG readings 4 times daily with no interval between readings exceeding 12-hours. Data from each 72-hour period will be analyzed for mean glucose concentration, mean glucose variability (absolute value of measured glucose minus 5.5 mmol/L [100 mg/dL]), number and duration of hyper- (> 10.0 mmol/L [180 mg/dL]) and hypo- (<3.0 mmol/L [54 mg/dL]) glycemic episodes, and total duration of hypoglycemia .

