# **Secondary Endpoints**

# **Efficacy Endpoints**

At  $75 \pm 5$  days following the first and final islet transplant:

- Proportion of insulin-independent subject
- The percent reduction in insulin requirements
- HbA1c
- Mean amplitude of glycemic excursions (MAGE)
- Glycemic lability index (LI)
- Ryan hypoglycemia severity (HYPO) score
- Basal (fasting) and 90-min glucose and c-peptide derived from the mixed-meal tolerance test (MMTT)
- β-score
- C-peptide: (glucose X creatinine) ratio
- Acute insulin response to glucose (AIRglu), insulin sensitivity, and disposition index derived from the insulin-modified frequently-sampled intravenous glucose tolerance (FSIGT) test
- Glucose variability and hypoglycemia duration derived from the continuous glucose monitoring system®
- Quality of life measures

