hypoglycemic unawareness, can have an HbA1c below 7%, yet the most chaotic and difficult glycemic control. Mean glucose values suffer the same problem in that swings in glucose values between 2 and 20 and back to 2 mmol/L may give a mean glucose of 8 mmol/L, a poor reflection of the real state of affairs.

Previous efforts at measuring glucose lability have ranged from qualitative to quantitative. Earlier definitions of brittle diabetes have incorporated visits to the hospital  $^{73,74}$  but these are subject to the vagaries of local practice. More quantitative measures have been the mean amplitude of glycemic excursions (MAGE) and the M value of Schlichtkrull Relief and an excursion of glucose readings over two days (a minimum of seven readings a day) and an amplitude is an excursion of glucose in excess of the standard deviation of the mean values for the day. If the mean of these amplitudes is  $\geq 11.1 \text{ mmol/L}$  the subject is considered to have labile diabetes. Where the MAGE fails as a measure of lability is with the subject who has a gradual decline in glucose over the day from 22 to 2 mmol/L. Such a profile will give a MAGE of 20 but such a gradual decline need not be considered truly labile.

Also used in the past has been the M value of Schlichtkrull but this logarithmic expression of the glucose deviation from a standard glucose level has not been validated. More recently the advent of continuous glucose monitoring system® (CGMS) has allowed insight into the patterns of glucose. The CGMS® profiles give exquisite details that have been quantified in terms of mean and standard deviation. Determining lability with this process has been more difficult and the suggested method has been the determination of the absolute value of measured glucose minus 5.5 mmol/L. This has the drawback that sustained high glucose levels will result in a high value but the profile may not necessarily be labile. In addition, the technique is currently limited to three days of monitoring and may be less accurate at low glucose levels.

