# 9.1 Metabolic Testing

# 9.1.1 Study Endpoints

Designated primary and secondary endpoints will be employed to compare subjects in this study to the group in CIT-07. Because the assessment of islet graft function is dependent on complex physiologic relationships between the graft and its recipient, no single test adequately addresses the viability of the transplant. Therefore, insulin-independence will be used as a clinically relevant measure of islet graft function for the primary endpoint, and additional stimulatory tests of islet graft function utilizing meal (MMTT) and glucose (FSIGT) challenges will be performed to assess secondary endpoints. Also, the effect of islet graft function on glycemic control (HbA1c), glycemic lability (MAGE and LI), hypoglycemia (Clarke and HYPO scores), glucose variability (CGMS), and QOL will be assessed as additional secondary endpoints.

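### The CGMS endpoint named glucose variability measures distance from 5.5 mmol/L, not spread, so a difference in mean glucose can be reported as a difference in variability

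*Protocol*

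**What the plan says.** The synopsis lists among the secondary efficacy endpoints at day 75 "Glucose variability and hypoglycemia duration derived from the continuous glucose monitoring system". Section 3.1.1 repeats this and adds CGMS to the day 365 list. Section 3.1.2 carries the measure into the hypothesis-generating endpoints, and section 9.1.1 confirms its status: "glucose variability (CGMS), and QOL will be assessed as additional secondary endpoints".

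Section 9.1.2.9 fixes the calculation. It begins "Data from each 72-hour period will be analyzed for mean glucose concentration, mean glucose variability" and gives the variability formula as the absolute difference from 5.5 mmol/L: "mean glucose variability (absolute value of measured glucose minus 5.5 mmol/L [100 mg/dL"]). The other outputs are the number and duration of hyperglycemic and hypoglycemic episodes and the total duration of hypoglycemia. No SD, coefficient of variation or other measure of spread within the trace is listed.

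Section 1.3.1 discusses the same formula. It reports that CGMS profiles "have been quantified in terms of mean and standard deviation", and that for lability "the suggested method has been the determination of the absolute value of measured glucose minus 5.5 mmol/L". It then adds: "This has the drawback that sustained high glucose levels will result in a high value but the profile may not necessarily be labile".

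**The concern.** An endpoint called variability should be zero for a flat trace and should rise with the size of the swings. This one does neither reliably. It rises with the glucose level, and the protocol's background section says so. Section 9 nevertheless adopts the formula without giving a reason and omits the SD.

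The practical risk lies in the comparison with CIT-07 (synopsis, Secondary Analyses; section 10.2.2). Section 1.1 describes the tacrolimus used there as toxic to β cells and expects better graft function without it, so a difference in mean glucose between the regimens is plausible. Under the present definition such a difference would also appear under the name glucose variability, whether or not the swings differed.

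**Working it through.** **Inputs.** The formula and the separate reporting of mean glucose come from section 9.1.2.9. The example of a swinging trace comes from section 1.3.1. I read the formula as averaged reading by reading, V = mean of |G − 5.5|, in mmol/L.

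**The protocol's own figure.** Section 1.3.1 says "swings in glucose values between 2 and 20 and back to 2 mmol/L may give a mean glucose of 8 mmol/L". Check: (2 + 20 + 2)/3 = 8.0. It reproduces.

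**What V contains.** For any trace,

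V = (mean G − 5.5) + 2 × mean of max(5.5 − G, 0).

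The second term is zero when all readings are at or above 5.5. V is then mean glucose minus 5.5 exactly and adds nothing to the mean. It carries other information only through readings below 5.5.

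**Examples** (SD over the readings shown):

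| Trace | Mean | SD | V |
|---|---|---|---|
| Flat 10.0 | 10.0 | 0 | 4.5 |
| Alternating 2 and 9 | 5.5 | 3.5 | (3.5 + 3.5)/2 = 3.5 |
| Alternating 6 and 14 | 10.0 | 4.0 | (0.5 + 8.5)/2 = 4.5 |
| 2, 20, 2 (section 1.3.1) | 8.0 | 8.5 | (3.5 + 14.5 + 3.5)/3 = 7.17 |
| Flat 12.67 | 12.67 | 0 | 7.17 |

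The flat trace at 10 scores above the 2/9 trace. Removing the 6/14 swings altogether does not change V. The protocol's own example of chaotic control scores the same as a flat trace at 12.67.

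**Limit of the reversal.** Since V is never smaller than |mean G − 5.5|, a flat trace never scores above a swinging trace with the same mean. It does so only when its level is high enough.

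**How far V repeats the mean.** The documents give no CGMS distributions, so cohorts were assumed: 3,000 simulated subjects each, with 864 autocorrelated lognormal readings per subject (72 hours at 5-minute intervals).

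| Assumed cohort mean (between-subject SD), mmol/L | Assumed within-subject CV | Correlation of V with mean | Correlation of V with SD |
|---|---|---|---|
| 9 (1.5) | 0.30–0.55 | 0.98 | 0.73 |
| 9 (2) | 0.30–0.55 | 0.97 | 0.74 |
| 8 (2) | 0.15–0.55 | 0.95 | 0.65 |
| 7 (1) | 0.15–0.40 | 0.91 | 0.66 |
| 6.5 (0.7) | 0.12–0.30 | 0.88 | 0.65 |
| 6 (0.5) | 0.12–0.45 | 0.57 | 0.89 |

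The overlap with the mean is strong at higher glucose levels. In the last cohort, near 6 mmol/L with a narrow spread between subjects, V follows the SD more closely than the mean.

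**The case against.** The best defence is that lability does not rest on this measure. Section 9.1.1 separates lability (MAGE and LI) from variability (CGMS), and section 9.1.2.3 assigns lability to MAGE and LI. Both are secondary endpoints computed from capillary readings, and Appendix 1 schedules them more often than CGMS. A reader might infer that the lability aim in section 2.2 depends on the CGMS formula, or that a real fall in swings would go unseen in the trial. Neither follows, because MAGE and LI are there to register it.

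A reader might also take section 1.3.1 as saying that the formula does not measure lability. It says less: it calls the formula the suggested method and warns that a high value need not mean a labile profile. It states a drawback of MAGE too.

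The other CGMS outputs separate some of the examples above. The 2/9 trace produces hypoglycemic episodes (below 3.0) and the 6/14 trace hyperglycemic ones (above 10.0), while flat 10.0 produces neither. Mean glucose is reported beside V, so an attentive reader could see when the mean drives a difference. The formula also has a cited published source. Section 10.2.2 already asks for extreme caution with nominally significant secondary results and says that power against CIT-07 is small.

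All of this stands and limits the harm. It does not make V a measure of spread. Episode counts at two thresholds are not a substitute for one, and separating variability from lability in words does not help when a flat trace can score high on variability.

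**Conclusion.** The point holds for this CGMS endpoint and its comparison with CIT-07. As defined, the endpoint does not measure what its name says. The identity with mean glucose for traces at or above 5.5 mmol/L, and the worked examples, are exact. The correlations rest on assumed cohorts and show only that the overlap is strong at higher means (0.95 to 0.98 at 8 to 9 mmol/L) and weaker near 6 (0.57), where well-functioning grafts may sit.

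A reader might infer that a flat trace generally outranks a swinging one; that is true only when the flat level is high enough. A reader might also score the section 1.3.1 example as an equal alternation of 2 and 20, but the stated mean of 8 rules that out, and the score is 7.17.

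The primary endpoint is unaffected. The change is worth making because the defect is fixed in the protocol text and the remedy is cheap.

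**What to change.** In section 9.1.2.9, define CGMS glucose variability as the within-subject SD of the 72-hour readings, with the coefficient of variation (SD divided by mean) alongside, at the CGMS visits already in Appendix 1 (baseline, day 75, day 365 and one year after the initial transplant). Keep the mean of |glucose − 5.5| under the label deviation from 5.5 mmol/L. For the comparison, compute the same quantities for the CIT-07 subjects whose CGMS traces are available; the CIT-07 definition and data are not in these documents, so this needs confirming.

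The cost is one definition and a few lines of code on traces this study already collects. The headline measure becomes less directly comparable with the cited CGMS report, which showing both quantities avoids.

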# 9.1.2.10 Quality of Life (QOL)

Generic and disease-specific measures will be used to assess quality of life.

## **Generic Measures**

Version 2 of the SF-36® Health Survey, standard (4-week) recall form

This widely used, generic instrument derives eight scales (physical functioning, role-physical, bodily pain, general health, vitality, social functioning, role-emotional, mental health) and two summary components (physical and mental). Changes to version 2 in relation to version 1 include simplified wording, simplified layout, and changes to the number of response options to selected items. Additionally, current normative data for version 2 are based on more recent, 1998 general US population data and norm-based scoring has been developed for the eight individual scales in addition to the summary components (for which it was available in version 1). The current manual contains US population norms by gender and age group within gender. The publisher states that the next printing, which is scheduled for the fall of 2005, will contain disease-specific norms including diabetes and kidney disease. If the 36-item version of the instrument were felt to be too lengthy, version 2 of the SF-12 (standard recall form) would be an option. This shorter version would derive eight scales and two summary components and would be also be normed to the 1998 data (general population and disease-specific groups).

## EQ-5D (EuroQoL)

This instrument is a utility measure that generates a descriptive profile and single index value for health status. The descriptive portion addresses five health dimensions (mobility, self care, usual activities, pain/discomfort, and anxiety/depression) with respondents indicating one of three possible responses for each dimension. Summary data can be reported as the proportion of respondents with problems in each dimension. Additionally, the multidimensional "health state" can be converted to a single weighted health status index that reflects the valuation of various possible health states from general population samples, including one that has been developed in a nationally representative US sample. The second portion of the EQ-5D is a (0-100) visual analogue scale that is used to report overall health status. Advantages of this instrument include its brevity and particular application in cost-effectiveness research. The EQ-5D is a public domain instrument. Projects may be registered and instruments obtained through the EQ-5D website, www.euroqol.org.

## **Disease-targeted Measures**

## **Diabetes Distress Scale**

The Diabetes Distress Scale (DDS) represents the latest iteration of the Problem Areas in Diabetes (PAID) scale. This is a 17-item self-administered questionnaire culled from a longer battery of 28 items. Psychometric properties for the DDS were recently published in Diabetes Care (March 2005). The DDS measures four diabetes-related distress domains: emotional-burden (EB), physician-related interpersonal distress (PD), regimen-related distress (RD), and diabetes-related interpersonal distress (ID). Internal consistency as measured by Cronbach's coefficient alpha ranged between 0.88 and 0.93 for the multi-item scales. The developers tested for and demonstrated construct validity using exploratory factor analysis.

# Hypoglycemic Fear Survey

The Hypoglycemic Fear Survey (HFS) is a 23-item self-administered survey for measuring the fear experienced with respect to hypoglycemia. The HFS measures hypoglycemia avoidance behavior and worry about hypoglycemia. Different versions of the instrument can be found in the literature, varying in length from 15 to 33 items. We have used the 33-item recommended by [name]. Coefficient alpha for the behavioral and the worry scales were found to exceed 0.90.

# 9.1.2.11 Glucose-potentiated arginine (GPA) test

## Rationale:

Both the glucose-potentiation slope and  $\beta$ -cell secretory capacity are  $\sim 25\%$  of normal in insulin-independent transplant recipients  suggesting the presence of a very limited engrafted mass even in successful cases. This is consistent with the increasing rate of return to insulin therapy that occurs with each year following successful transplantation. Transplantation strategies that improve the engrafted  $\beta$ -cell mass should be identified by an increased  $\beta$ -cell secretory capacity in insulin-independent recipients, and should allow for more durable graft survival. Alternatively, immunosuppressive strategies that are free of calcineurin-inhibitors may lead to further improvements of both the glucose-potentiation slope and  $\beta$ -cell secretory capacity since calcineurin-inhibitors impair glucose-dependent insulin secretion and reduce  $\beta$ -cell insulin content

### Approach:

The standard IV arginine stimulation test (AST) involves blood sampling at baseline (t = -5 & -1 min) and at t = 2, 3, 4, & 5 min post-injection of a maximally stimulating dose of arginine hydrochloride (5 g or 50 mL of 10% solution, Pharmacia & Upjohn, Kalamazoo, MI) over 1 min starting at t = 0. After collection, the protease inhibitors trasylol and leupeptin are immediately added to the blood samples, which are placed on ice, centrifuged at 4 °C, and frozen at -80 °C until biochemical analysis. The acute C-peptide and insulin responses to arginine (ACRarg & AIRarg), defined as the mean of the post-injection C-peptide or insulin values minus the mean of their baseline values, provide measures of  $\beta$ -cell function. The total amount of blood sampled is 24 mL.

The AST may be extended to a glucose-potentiated arginine (GPA) test. This will only be done in insulin-independent subjects or those taking  $\leq 0.1$  U/kg of insulin daily to optimize their glycemic control. After the baseline AST described above, a hyperglycemic clamp technique utilizing a variable rate of 20% and 10% glucose solutions is performed to achieve a glucose

level of 230 mg/dL. Blood samples are taken every 5 min, centrifuged, and measured at bedside with a portable glucose analyzer (YSI 1500 Sidekick; Yellow Springs Instruments, Yellow Springs, OH) in order to adjust the infusion rates and achieve the desired glucose concentration. After 45-minutes of the glucose infusion, the 5 g arginine pulse is injected again with identical blood sampling. It has been demonstrated that the first administration of arginine has no effect on the subsequent response to arginine using this protocol. Then, a 2-hour period without glucose infusion takes place to avoid the priming effects of hyperglycemia on insulin release. At the end of the 2-hour period, a hyperglycemic clamp is performed to achieve a glucose level of 340 mg/dL. Forty-five minutes after initiation of the glucose infusion, another arginine pulse is injected with identical blood sampling. The total amount of blood sampled is 92 mL.

The AIRarg performed during the 230 mg/dL glucose clamp allow for determination of the glucose-potentiation slope, a measure of glucose-dependent insulin secretion, defined as the difference in the AIRarg at fasted and 230 mg/dL glucose levels, divided by the difference in glucose ( $\Delta$ AIRarg/ $\Delta$  PG). The AIRarg performed during the 340 mg/dL glucose clamp allows for estimation of the  $\beta$ -cell secretory capacity (AIRmax), a measure of functional  $\beta$ -cell mass, since the AIRarg is maximal at glucose concentrations > 315 mg/dL. The same calculations can be performed using ACRarg.

